- i Set the significance level $\alpha = 0.01$, which will be used to detect outliers.
- ii No more than 5% of sample results can be flagged as outliers. Set the upper bound on number of potential outliers (h) at this 5% level, rounding down to a whole number ($h = 6$ for 120 samples).
- iii Determine if one or more suspect results could be outliers based upon the generalized Extreme Studentized Deviate (ESD) test.
 - 5) Compute the average bias across all the specimens (\bar{d}) and the SD corresponding to the bias.
 - 6) Find the maximum scaled difference (ESD_1) as follows:
$$ESD_1 = \max |d_j - \bar{d}| / SD \quad \text{for } j = 1, 2, \dots, n$$
- 7) Repeat this calculation to obtain the ESD_i for all potential outliers ($i = 1, 2, \dots, h$). Each subsequent calculation of ESD_i is performed after removing the previously identified potential outlier from the dataset. Thus at each iteration the number of results is reduced by one, then \bar{d} , SD, and the maximum scaled difference (ESD_i) are computed again (ie, to look for outlier 2, the number of samples remaining is $j = 1, 2, \dots, n-1$).
- 8) For $i = 1, 2, \dots, h$, compute the following critical values:

$$\lambda_i = \frac{t_{v,p} (n - 1)}{\sqrt{(n - i + 1)(v + t_{v,p}^2)}}$$

where

n = the initial number of samples in the dataset

$i = 1, 2, \dots, h$

$v = n - i - 1$

$$p = \frac{\alpha}{2(n - i + 1)}$$

$t_{v,p}$ = 100p percentage point from Student's t distribution with v , degrees of freedom and probability = p .

- iv The number of outliers is determined by finding the largest i such that $ESD_i > \lambda_i$.

h. Acceptance Criteria

For method comparison, acceptance criterion will be applied to Passing-Bablok regression result for the single replicate result from the i-STAT 500 vs. the single replicate result from the i-STAT 1 Wireless for the entire measuring interval. Samples across the measuring interval of 100 – 180 mmol/L shall have a regression slope of 1.0 ± 0.05 and correlation coefficient (r) ≥ 0.95 (DIR-001, CartP_74).

CONFIDENTIAL INFORMATION

There is no acceptance criterion for other analyses. The information is intended to be reported in regulatory submission(s) and/or product labeling.

IV. References

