It is expected that specimen collection will be completed at different times for each of the three assays (sodium, glucose and hematocrit) during the study. The data for a given assay may be analyzed against acceptance criteria once the specimen collection for that assay has been completed and may be used for different regulatory submissions (i.e. FDA response or 510(k) submission). Once specimen collection is determined to be completed, additional specimens will not be collected for that assay unless requested by a regulatory agency.

Interim data for a given assay (before specimen collection is completed) will not be evaluated against acceptance criteria. Interim data monitoring will be conducted to ensure the data meets validity criteria and minimum sample size requirements.

CONFIDENTIAL INFORMATION

III. Statistical Procedures

Refer to the clinical evaluation protocol for the objective of the study, study design, and for additional details on data handling conventions. This section contains additional details about the analyses in the clinical study plan, as well as other additional analyses needed for the regulatory submission(s).

A. Method Comparison

1. Glucose

a. Study Design

Method comparison testing will be performed using whole blood capillary specimens prospectively collected from routine patient care. This testing will be performed at a minimum of 3 sites. Testing of approximately 120 native and altered specimens will be performed in singlicate on both the i-STAT 500 analyzer and the i-STAT 1 Wireless analyzer. One (1) i-STAT 500 and one (1) i-STAT 1 Wireless analyzer will be used for this testing. Each site should collect and test a minimum of 40 specimens until sufficient specimens are collected and tested for study analysis. A minimum of one lot of i-STAT EC4+ cartridges will be used for this testing.

b. Analysis Variables

The analysis variable for the method comparison study is the i-STAT EC4+ cartridge glucose concentration values (mg/dL).

c. Sample Size

The sample size is based on the recommendation of CLSI EP09-A3.

A minimum of 120 capillary whole blood specimens covering the measuring interval will be collected from a minimum of 3 sites. Each site should collect a minimum of 40 specimens.

Minimum of 3 sites

Within each site:

Number of lots = 1

i-STAT 1 Wireless analyzers = 1

i-STAT 500 analyzers = 1

Replicates per specimen = 1

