e. Level of Significance

Two-sided confidence intervals will be calculated at a 95% confidence level.

f. Data Handling Convention

All results from this testing that are performed according to the protocol and not excluded by the reviewers will be eligible for analysis. Reasons for any excluded results will be captured in the study database.

- Exclude the specimen from analysis if no results can be obtained from either the i-STAT 1 Wireless or the i-STAT 500.
- Exclude test results if there is an assignable cause.
- Exclude the specimen if the glucose concentration value is outside of the measuring interval on either analyzer.
- Exclude a second valid result obtained due to a repeat test of the same specimen for another analyte. These results will be excluded with the reason “Additional test for other analyte. Repeat testing produces results for all analytes on cartridge.”
- Exclude a result obtained from a subject that is for a bucket that is already filled with the reason “Not part of analysis.”

g. Outliers

The outlier criteria below are based on CLSI document EP09-A3 Appendix B. The generalized Extreme Studentized Deviate (ESD) technique will be used to detect the outlier.

The generalized Extreme Studentized Deviate (ESD) technique assumes that the distribution of the vast majority of data points is normal (Gaussian), can be used when the number of outliers is unknown and becomes more robust as the number of samples increases. To perform this technique:

CONFIDENTIAL INFORMATION

- i Set the significance level $\alpha = 0.01$, which will be used to detect outliers.
- ii No more than 5% of sample results can be flagged as outliers. Set the upper bound on number of potential outliers (h) at this 5% level, rounding down to a whole number ($h = 6$ for 120 samples).
- iii Determine if one or more suspect results could be outliers based upon the generalized Extreme Studentized Deviate (ESD) test.
 - 1) Compute the average bias across all the specimens (\bar{d}) and the SD corresponding to the bias.
 - 2) Find the maximum scaled difference (ESD_1) as follows:
$$ESD_1 = \max |d_j - \bar{d}| / SD \quad \text{for } j = 1, 2, \dots, n$$

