 - 3) Repeat this calculation to obtain the ESD_i for all potential outliers ($i = 1, 2, \dots, h$). Each subsequent calculation of ESD_i is performed after removing the previously identified potential outlier from the dataset. Thus at each iteration the number of results is reduced by one, then \bar{d} , SD, and the maximum scaled difference (ESD_i) are computed again (ie, to look for outlier 2, the number of samples remaining is $j = 1, 2, \dots, n-1$).
 - 4) For $i = 1, 2, \dots, h$, compute the following critical values:

$$\lambda_i = \frac{t_{v,p} (n - 1)}{\sqrt{(n - i + 1)(v + t_{v,p}^2)}}$$

where

n = the initial number of samples in the dataset

$i = 1, 2, \dots, h$

$v = n - i - 1$

$$p = \frac{\alpha}{2(n - i + 1)}$$

$t_{v,p}$ = 100p percentage point from Student's t distribution with v , degrees of freedom and probability = p .

- iv The number of outliers is determined by finding the largest i such that $ESD_i > \lambda_i$.

h. Acceptance Criteria

For method comparison, acceptance criterion will be applied to Passing-Bablok regression result for the single replicate result from the i-STAT 500 vs. the single replicate result from the i-STAT 1 Wireless for the entire measuring interval. Samples across the measuring interval of 20 – 700 mg/dL shall have a regression slope of 1.0 ± 0.05 and correlation coefficient (r) ≥ 0.95 (DIR-001, CartP_121).

CONFIDENTIAL INFORMATION

There is no acceptance criterion for other analyses. The information is intended to be reported in regulatory submission(s) and/or product labeling.

2. Hematocrit

a. Study Design

Method comparison testing will be performed using whole blood capillary specimens prospectively collected from routine patient care. This testing will be performed at a minimum of 3 sites. Testing of approximately 120 native and altered specimens will be performed in singlicate on both the i-STAT 500 analyzer and the i-STAT 1 Wireless analyzer. One (1) i-STAT 500 and one (1) i-STAT 1 Wireless analyzer will be used for this testing. Each site should collect and test a minimum of 40 specimens until sufficient specimens are collected and tested for study analysis. A minimum of one lot of i-STAT EC4+ cartridges will be used for this testing.

b. Analysis Variables

The analysis variable for the method comparison study is the i-STAT EC4+ cartridge hematocrit values (%PCV).

c. Sample Size

The sample size is based on the recommendation of CLSI EP09-A3.

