A minimum of 120 whole blood capillary specimens covering the measuring interval will be collected from a minimum of 3 sites. Each site should collect a minimum of 40 specimens.

Minimum of 3 sites

Within each site:

Number of lots = 1

i-STAT 1 Wireless analyzers = 1

i-STAT 500 analyzers = 1

Replicates per specimen= 1

An estimated distribution of specimen target levels for hematocrit by site is presented in the chart below:

CONFIDENTIAL INFORMATION

Hct (%PCV)	~ # Sample /Site	Target Proportion
< 27	6	15%
27 – 35	10	25%
36 – 50	20	50%
> 50	4	10%
Total	40	

No hematocrit range shall have greater than 10% above the target proportion. Hematocrit results from samples that would cause a given hematocrit range to have a greater proportion of samples beyond the maximum allowed proportion will be excluded from this analysis. The hematocrit results from samples with earlier collection dates and times will be included.

d. Statistical Analysis Method

Perform the following analyses for the single replicate of the i-STAT 500 result versus the single replicate of the i-STAT 1 Wireless result. Analyses will be done with outliers and without outliers if any outliers are identified.

- For each site as well as all sites combined, calculate the correlation coefficient and perform the Deming regression and Passing-Bablok regression analyses on the concentration values (the i-STAT 500 result as dependent variable versus the i-STAT 1 Wireless result as independent variable) and provide estimates and 95% CIs of the slope and intercept from the regression analysis.
- For each site as well as all sites combined, generate scatter plots of the concentration values of the i-STAT 500 result (y-axis) versus the concentration values of the i-STAT 1 Wireless result (x-axis). The line of identity ($y = x$) and descriptive statistics will be presented in the scatter plots.
- For each site as well as all sites combined, generate Bland-Altman bias plots and Bland-Altman percent bias plots. Calculate the difference between the i-STAT 500 concentration value (y) and the i-STAT 1 Wireless concentration value (x), $y - x$. Also calculate $(y + x) / 2$. Plot the difference between y and x, $y - x$, against their mean $(y + x) / 2$ (Bland-Altman bias plot); Plot the percent difference between y and x, $100 \times (y - x) / x$, against their mean $(y + x) / 2$ (Bland-Altman percent bias plot).

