- Using the regression equation for each site separately and for all sites combined, calculate the predicted bias (difference) between the i-STAT 500

CONFIDENTIAL INFORMATION

results and the i-STAT 1 Wireless results at the medical decision points (33, 53, 56, 70 %PCV) and their 95% CIs. If gender information is collected, the medical decision point of 53 %PCV will be analyzed with only females and the medical decision point of 56 %PCV will be analyzed with only males. The calculation of predicted bias and its 95% CI calculation are based on CLSI EP09-A3.

e. Level of Significance

Two-sided confidence intervals will be calculated at a 95% confidence level.

f. Data Handling Convention

All results from this testing that are performed according to the protocol and not excluded by the reviewers will be eligible for analysis. Reasons for any excluded results will be captured in the study database.

- Exclude the specimen from analysis if no results can be obtained from either the i-STAT 1 Wireless or the i-STAT 500.
- Exclude test results if there is an assignable cause.
- Exclude any specimen if the hematocrit value is outside of the measuring interval on either analyzer.
- Exclude a second valid result obtained due to a repeat test of the same specimen for another analyte. These results will be excluded with the reason “Additional test for other analyte. Repeat testing produces results for all analytes on cartridge.”
- Exclude a result obtained from a subject that is for a bucket that is already filled with the reason “Not part of analysis.”

g. Outliers

The outlier criteria below are based on CLSI document EP09-A3 Appendix B. The generalized Extreme Studentized Deviate (ESD) technique will be used to detect outliers.

The generalized Extreme Studentized Deviate (ESD) technique assumes that the distribution of the vast majority of data points is normal (Gaussian), can be used when the number of outliers is unknown and becomes more robust as the number of samples increases. To perform this technique:

CONFIDENTIAL INFORMATION

- i Set the significance level $\alpha = 0.01$, which will be used to detect outliers.
- ii No more than 5% of sample results can be flagged as outliers. Set the upper bound on number of potential outliers (h) at this 5% level, rounding down to a whole number ($h = 8$ for 160 samples).
- iii Determine if one or more suspect results could be outliers based upon the generalized Extreme Studentized Deviate (ESD) test.

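### The printed ESD critical value is right only at the first step: its numerator should be (n - i), not (n - 1), so later steps are conservative and multiple outliers are under-detected

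*SAP*

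**What the plan says.** The Outliers sections of the SAP (III.A.1.g glucose, III.A.2.g hematocrit, III.A.3.g sodium) give the same procedure. The level is fixed first: "Set the significance level $\alpha = 0.01$, which will be used to detect outliers". At most 5% of results may be flagged, rounded down, which gives a cap h of 6 for 120 samples.

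At each step the most extreme difference is removed and the mean, SD and statistic are recomputed: "Thus at each iteration the number of results is reduced by one". The statistic at step i is compared with

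lambda_i = t (n - 1) / sqrt[(n - i + 1)(v + t²)], with v = n - i - 1 and p = alpha / [2(n - i + 1)],

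where "n = the initial number of samples in the dataset". The number of outliers is the largest i at which the statistic exceeds lambda_i. The analyses are then run with and without any outliers found. Section IX.B.7 of the protocol names the ESD technique but gives no formula.

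**The concern.** At step i, m = n - i + 1 results remain. Three parts of the formula use m: the first factor under the root is m, v is m - 2, and p is alpha/(2m). The numerator alone does not, because n is defined as the starting count. The formula is therefore at odds with its own definitions from step 2 onward.

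The generalized ESD test is used because several outliers can mask one another, and its decision rule takes the largest step that passes. The later critical values decide that case, and those are the values affected. The consequences would be a flagged set that does not match the stated alpha, altered results in the analyses without outliers, and a possible mismatch between a program that follows the SAP and one that uses the m-sample critical value at each step.

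**Working it through.** **Inputs.** From the SAP Outliers sections: alpha = 0.01, h = 6 at n = 120, and the formula and definitions above. From the SAP Sample Size sections: at least 120 specimens in all and 40 per site.

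**Deriving the critical value.** Let R = |d - mean|/SD for one of m results. The t statistic that compares that result with the other m - 1 is

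t = R sqrt{ m(m - 2) / [(m - 1)² - mR²] }, on m - 2 degrees of freedom.

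Solving for R gives

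R = (m - 1) t / sqrt[ m(m - 2 + t²) ].

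With m = n - i + 1, the denominator and v match the SAP, and p = alpha/(2m) is the matching two-sided allowance for m candidates. The numerator is m - 1 = n - i. The printed value is therefore too high by the factor (n - 1)/(n - i), which is 1 only at i = 1.

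**Check on limits.** R cannot exceed (m - 1)/sqrt(m). As t grows, the printed value tends to (n - 1)/sqrt(m), which lies above that ceiling whenever i > 1. The printed form is therefore not an alternative valid version.

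**Step 6 at n = 120.** m = 115, v = 113, p = 0.01/230, upper-tail t = 4.0715. The denominator is sqrt[115 × (113 + 16.577)] = 122.07.
- Printed: 4.0715 × 119 / 122.07 = 3.969.
- Correct: 4.0715 × 114 / 122.07 = 3.802.
- Ratio: 119/114 = 1.044.

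**All steps at n = 120.** The implied alpha comes from putting the printed lambda into the t formula above and taking 2m times the upper tail.

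| Step | Printed lambda | Correct lambda | Implied alpha, printed |
|---|---|---|---|
| 1 | 3.817 | 3.817 | 0.0100 |
| 2 | 3.846 | 3.814 | 0.0086 |
| 3 | 3.876 | 3.811 | 0.0074 |
| 4 | 3.907 | 3.808 | 0.0063 |
| 5 | 3.938 | 3.805 | 0.0054 |
| 6 | 3.969 | 3.802 | 0.0046 |

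The stated 0.01 is reproduced at step 1 only under the printed form, and at every step with (n - i). Simulation of 400,000 normal samples per step agrees. The printed form gives 0.0099, 0.0087, 0.0062 and 0.0045 at steps 1, 2, 4 and 6; (n - i) gives 0.0099, 0.0101, 0.0101 and 0.0100. If the test is run on one site of 40 (h = 2), the step-2 alpha is 0.0063.

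**Whole procedure.** With no outliers, the chance of any flag is 0.0103 under both forms (200,000 simulated studies at n = 120). With outliers, the size and direction of the shift must be assumed. The table uses n = 120 and outliers all shifted 5 SD the same way. The range in the first two result columns is the spread over repeated simulations.

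| True outliers | All flagged, printed | All flagged, correct | Share found, printed | Share found, correct |
|---|---|---|---|---|
| 1 | 82% | 82% | 81.5% | 81.5% |
| 2 | 64–66% | 66–68% | 79.0% | 79.9% |
| 3 | 50–52% | 54–55% | 76.1% | 78.3% |
| 6 | 21–22% | 32% | 60.1% | 69.4% |

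For six outliers at other shifts, all are flagged (printed against correct) in 6.6% against 11.9% at 4.5 SD, 47.8% against 58.0% at 5.5 SD, and 74.5% against 82.3% at 6 SD.

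**The case against.** **The slip may not be the author's.** The difference is one character, 1 against i, in a formula read from PDF by a program, and the three sections are near copies. The same form in all three, beside correctly read i's elsewhere in the formula, makes a misreading less likely but does not exclude it. This stands as a reason to look at the source and the code first. It does not make the text as given correct. The SAP attributes its criteria to CLSI EP09-A3 Appendix B, which is not available here, but the derivation does not depend on it.

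**The loss is concentrated near the cap.** This stands. It is nil for one outlier, one to two points in the share found for two or three, and about nine points for six.

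**The consequence is bounded.** Results are also reported with outliers kept, and under-flagging leaves discrepant pairs in, which is generally the less favourable direction for the sponsor. Simulations of 1,000 studies per scenario used the SAP's glucose and sodium distributions, 5 SD outliers, and assumed SDs of differences of 8 mg/dL for glucose and 1.5 or 3 mmol/L for sodium. The verdict on slope and correlation changed in none, except with six outliers and a sodium SD of 3 (7 of 1,000). This also stands, although the Acceptance Criteria sections do not say whether the run with or without outliers is the one judged.

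**Hematocrit cap.** A reader might infer from the cap of 8 "for 160 samples" that hematocrit breaches the 5% limit, since its Sample Size section asks for "A minimum of 120 whole blood capillary specimens covering the measuring interval". The text does not support that. The example is correct (0.05 × 160 = 8), 120 is a minimum, and the operative rule is 5% rounded down, which gives 6 at 120.

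**Conclusion.** The printed critical value is wrong as written from step 2 onward in all three assays. At n = 120 it is too high by 0.85% at step 2 and 4.4% at step 6, and the step-wise alpha falls from 0.01 to 0.0046. The lambda and alpha figures need only the SAP's own inputs and normal differences, which the SAP assumes for the vast majority of points. The detection losses also rest on the assumed shifts.

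A reader might go further and infer that the outlier test fails to hold its overall level, or that acceptance decisions are unsafe. Neither is supported. The false-flag rate with no outliers stays about 0.01, the later steps err on the conservative side, and any effect on the acceptance verdict is likely small. This is a correction that should be made, not a threat to the study's conclusions.

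**What to change.** 1. Check the numerator in the source SAP and in the analysis program.
2. If either has (n - 1), replace it with (n - i) in III.A.1.g, III.A.2.g and III.A.3.g and in the code.
3. State that t is the upper-tail point. The SAP calls it the 100p percentage point, with p = alpha/[2(n - i + 1)]. Taken as a lower percentile, that would make lambda negative (-3.82 at step 1), and all h candidates would be flagged.

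The hematocrit example needs no correction. The cost is a short text change and a program check, with no effect on specimens, sites or timelines.

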#### **6. Data Handling Convention**

All results from this testing that are performed according to the protocol and not excluded by the reviewers will be eligible for analysis. Reasons for any excluded results will be captured in the study database.

- Exclude the specimen from analysis if no results can be obtained from either the i-STAT 1 Wireless or the i-STAT 500.
- Exclude test results if there is an assignable cause.
- Exclude the specimen if the analyte value of interest (e.g., glucose, hematocrit or sodium) is outside of the measuring interval on either analyzer.

- Exclude a result obtained from a subject that is for a bucket of a given analyte that is already filled with the reason “Not part of analysis.”

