A suggested distribution of specimen target levels for glucose by site is presented in the chart below:

CONFIDENTIAL INFORMATION

Glucose (mg/dL)	~ # Sample /Site	Max # Samples /Site
≤ 50	2	4
> 50-80	4	8
> 80-120	8	14
> 120-200	12	20
> 200-300	6	12
> 300-400	4	8
> 400-500	2	4
>500	2	4
Total	40	

If more than the maximum allowed number of samples is collected for a given glucose range within a site, the glucose result from samples with the earlier collection date and time will be included in the analysis. The glucose results for samples collected beyond the maximum allowed number of samples will not be used for this analysis.

d. Statistical Analysis Method

Perform the following analyses for the single replicate of the i-STAT 500 result versus the single replicate of the i-STAT 1 Wireless result. Analyses will be done with outliers and without outliers if any outliers are identified.

- For each site as well as all sites combined, calculate the correlation coefficient and perform the Deming regression and Passing-Bablok regression analyses on the concentration values (the i-STAT 500 result as dependent variable versus the i-STAT 1 Wireless result as independent variable) and provide estimates and 95% CIs of the slope and intercept from the regression analysis.
- For each site as well as all sites combined, generate scatter plots of the concentration values of the i-STAT 500 result (y-axis) versus the concentration values of the i-STAT 1 Wireless result (x-axis). The line of identity ($y = x$) and descriptive statistics will be presented in the scatter plots.
- For each site as well as all sites combined, generate Bland-Altman bias plots and Bland-Altman percent bias plots. Calculate the difference between the i-STAT 500 concentration value (y) and the i-STAT 1 Wireless concentration value (x), $y - x$. Also calculate $(y + x) / 2$. Plot the difference between y and x, $y - x$, against their mean $(y + x) / 2$ (Bland-Altman bias plot); Plot the

CONFIDENTIAL INFORMATION

percent difference between y and x, $100 \times (y - x) / x$, against their mean $(y + x) / 2$ (Bland-Altman percent bias plot).

- Using the regression equation for each site separately and for all sites combined, calculate the predicted bias (difference) between the i-STAT 500 results and the i-STAT 1 Wireless results at the medical decision points (45, 120, 180 mg/dL) and their 95% CIs. The calculation of predicted bias and its 95% CI calculation are based on CLSI EP09-A3.

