 - 1) Compute the average bias across all the specimens (\bar{d}) and the SD corresponding to the bias.
 - 2) Find the maximum scaled difference (ESD_1) as follows:
$$ESD_1 = \max |d_j - \bar{d}| / SD \quad \text{for } j = 1, 2, \dots, n$$
- 3) Repeat this calculation to obtain the ESD_i for all potential outliers ($i = 1, 2, \dots, h$). Each subsequent calculation of ESD_i is performed after removing the previously identified potential outlier from the dataset. Thus at each iteration the number of results is reduced by one, then \bar{d} , SD, and the maximum scaled difference (ESD_i) are computed again (ie, to look for outlier 2, the number of samples remaining is $j = 1, 2, \dots, n-1$).
- 4) For $i = 1, 2, \dots, h$, compute the following critical values:

$$\lambda_i = \frac{t_{v,p} (n - 1)}{\sqrt{(n - i + 1)(v + t_{v,p}^2)}}$$

where

n = the initial number of samples in the dataset

$i = 1, 2, \dots, h$

$v = n - i - 1$

$$p = \frac{\alpha}{2(n - i + 1)}$$

$t_{v,p}$ = 100p percentage point from Student's t distribution with v , degrees of freedom and probability = p .

- iv The number of outliers is determined by finding the largest i such that $ESD_i > \lambda_i$.

h. Acceptance Criteria

For method comparison, acceptance criterion will be applied to Passing-Bablok regression result for the single replicate result from the i-STAT 500 vs. the single replicate result from the i-STAT 1 Wireless for the entire measuring interval. Samples across the measuring interval shall have a regression slope of 1.0 ± 0.054 and correlation coefficient (r) ≥ 0.95 (DIR-001, CartP_145).

CONFIDENTIAL INFORMATION

There is no acceptance criterion for other analyses. The information is intended to be reported in regulatory submission(s) and/or product labeling.

3. Sodium

a. Study Design

Method comparison testing will be performed using whole blood capillary specimens prospectively collected from routine patient care. This testing will be performed at a minimum of 3 sites. Testing of approximately 120 native and altered specimens will be performed in singlicate on both the i-STAT 500 analyzer and the i-STAT 1 Wireless analyzer. One (1) i-STAT 500 and one (1) i-STAT 1 Wireless analyzer will be used for this testing. Each site should collect and test a minimum of 40 specimens until sufficient specimens are collected and tested for study analysis. A minimum of one lot of i-STAT EC4+ cartridges will be used for this testing.

b. Analysis Variables

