The analysis variable for the method comparison study is the i-STAT EC4+ cartridge sodium concentration values (mmol/L).

c. Sample Size

The sample size is based on the recommendation of CLSI EP09-A3.

A minimum of 120 capillary whole blood specimens covering the measuring interval will be collected from a minimum of 3 sites. Each site should collect a minimum of 40 specimens.

Minimum of 3 sites

Within each site:

Number of lots = 1

i-STAT 1 Wireless analyzers = 1

i-STAT 500 analyzers = 1

Replicates per specimen = 1

A suggested distribution of specimen target levels for sodium by site is presented in the chart below:

CONFIDENTIAL INFORMATION

Sodium (mmol/L)	~ # Sample /Site	Max # Samples /Site
≤ 130	8	14
> 130-140	16	24
> 140-150	12	20
> 150	4	8
Total	40	

If more than the maximum allowed number of samples is collected for a given sodium range within a site, the sodium result from samples with the earlier collection date and time will be included in the analysis. The sodium results for samples collected beyond the maximum allowed number of samples will not be used for this analysis.

d. Statistical Analysis Method

Perform the following analyses for the single replicate of the i-STAT 500 result versus the single replicate of the i-STAT 1 Wireless result. Analyses will be done with outliers and without outliers if any outliers are identified.

- For each site as well as all sites combined, calculate the correlation coefficient and perform the Deming regression and Passing-Bablok regression analyses on the concentration values (the i-STAT 500 result as dependent variable versus the i-STAT 1 Wireless result as independent variable) and provide estimates and 95% CIs of the slope and intercept from the regression analysis.
- For each site as well as all sites combined, generate scatter plots of the concentration values of the i-STAT 500 result (y-axis) versus the concentration values of the i-STAT 1 Wireless result (x-axis). The line of identity ($y = x$) and descriptive statistics will be presented in the scatter plots.

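### Does the hematocrit range cap of 10% above target need its unit (percentage points or relative) written into the SAP?

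*SAP*

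**What the plan says.** The hematocrit chart in SAP III.A.2.c gives approximate counts per site of 6, 10, 20 and 4 (total 40) for <27, 27-35, 36-50 and >50 %PCV, with target proportions of 15%, 25%, 50% and 10%. The cap reads "No hematocrit range shall have greater than 10% above the target proportion". Results from "samples that would cause a given hematocrit range to have a greater proportion of samples beyond the maximum allowed proportion will be excluded", and earlier-collected results are kept.

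Glucose (SAP III.A.1.c) and sodium (SAP III.A.3.c) are handled differently. Each has a column of whole-number maxima per site, and the exclusion rule begins "If more than the maximum allowed number of samples is collected for a given glucose range within a site" or, for sodium, "If more than the maximum allowed number of samples is collected for a given sodium range within a site".

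Two data-handling rules lean on the cap. SAP III.A.2.f says "Exclude a result obtained from a subject that is for a bucket that is already filled", and Protocol IX.B.6 says "Exclude a result obtained from a subject that is for a bucket of a given analyte that is already filled". The set that remains feeds the only hematocrit acceptance criteria (SAP III.A.2.h): "Samples across the measuring interval shall have a regression slope of" 1.0 ± 0.054, with r ≥ 0.95. SAP II adds: "Once specimen collection is determined to be completed, additional specimens will not be collected for that assay unless requested by a regulatory agency".

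**The concern.** Because the targets are themselves percentages, 10% above 15% can be read as 25% or as 16.5%. Neither document states the unit. Hematocrit also has no numeric maximum to define a filled range, and the rule lacks the within-site wording used for the other two analytes.

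The current Protocol plans about 100 specimens per site against a chart of 40, so overfilled ranges are foreseeable. The cap then decides which pairs are analysed, how many count towards the minimum of 120, and how wide a spread of values supports r. A tighter cap on the middle range keeps a wider spread and so a higher r. If the unit were settled only after results were seen, it could be chosen to favour a pass. Once collection closes, a shortfall could be made good only at a regulator's request.

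**Working it through.** **Inputs.** Targets and counts are from SAP III.A.2.c, and the minimum of 120 from SAP III.A.2.c and Protocol III.A. The figure of about 100 specimens per site is from Protocol III.A, VI.C.1.a.i and IX.B.1. Collected mixes, error SDs and the limits of the outer ranges are assumptions, because the documents give none. Mixes are in the order <27 / 27-35 / 36-50 / >50.

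**The plan's own figures.** 6/40, 10/40, 20/40 and 4/40 give 15, 25, 50 and 10%, and 3 × 40 = 120. Both reproduce.

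**Caps under each reading.**

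| Range | Target | Points (target + 10) | Relative (target × 1.1) | Max of 40, points | Max of 40, relative |
|---|---|---|---|---|---|
| <27 | 15% (6) | 25% | 16.5% | 10 | 6 |
| 27-35 | 25% (10) | 35% | 27.5% | 14 | 11 |
| 36-50 | 50% (20) | 60% | 55% | 24 | 22 |
| >50 | 10% (4) | 20% | 11% | 8 | 4 |

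**Which reading fits the rest of the SAP.**

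- The sodium maxima over target are 14/8, 24/16, 20/12 and 8/4, or 1.75, 1.5, 1.67 and 2. The glucose ratios run from 20/12 = 1.67 to 2. A relative hematocrit cap would be 1.1.
- Sodium's range with a 10% target (4 of 40) has a maximum of 8. The points reading also gives 8 for hematocrit's 10% range; the relative reading gives 4.
- The relative reading allows exactly the target count in <27 and >50, although the chart calls its counts approximate.
- Under the relative reading a site with no specimen below 27 has no compliant set at all, since 27.5 + 55 + 11 = 93.5%, short of 100%.

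**How far the analysed sets differ.** Caps are applied by site to the analysed set, keeping the largest compliant set. Example, 6/20/70/4 per 100:

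- Points: the 30 specimens outside 36-50 must be at least 40% of the set, so n = 30/0.40 = 75 per site, or 225 in all.
- Relative: the 10 specimens outside 27-50 must be at least 100 − 27.5 − 55 = 17.5%, so n ≤ 10/0.175 = 57.1. With whole-number limits the largest compliant set is 55 (6 + 15 + 30 + 4), or 165 in all.
- To reach 120 analysed: 120/0.75 = 160 specimens under points; 120/(0.10/0.175) = 210 under relative.

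| Mix per 100 | Kept of 300, points v relative | Collect for 120, points v relative |
|---|---|---|
| 10/25/60/5 | 300 v 252 | 120 v 140 |
| 6/20/70/4 | 225 v 165 | 160 v 210 |
| 4/15/78/3 | 165 v 120 | 218 v 300 |
| 3/15/80/2 | 150 v 78 | 240 v 420 |

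Under points every mix reaches 120 within the roughly 300 planned. Only the most skewed mix splits the readings on the minimum. At 12/25/55/8 and 14/24/53/9 both keep all 100 per site, and at 6/10/20/4 both keep all 40.

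**Pass/fail.** The simulation used three sites of 100, no true bias, equal independent error on each analyzer and results rounded to 1 %PCV. A pass needed r ≥ 0.95 and a Passing-Bablok slope within 1 ± 0.054. There were 600 runs per cell with true values of 20-60 %PCV, and 150 runs per cell with the outer ranges extended to 15 and 70. The 70 follows the SAP's highest hematocrit decision point (III.A.2.d); the 15 is an assumption. Disagreement between readings at error SDs of 1.7/1.8/1.9 %PCV:

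| Mix | True values 20-60 | True values 15-70 |
|---|---|---|
| 10/25/60/5 | 6/30/38% | 0/0/5% |
| 6/20/70/4 | 16/48/54% | 0/1/8% |
| 4/15/78/3 | 23/45/49% | 0/7/22% |

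At SDs of 1.0 to 1.5 with 20-60, disagreement is 0-1% for these three mixes. With 15-70 the sensitive window moves to SD 2.0 or above (17-39% there). Disagreement is material only where r falls within about 0.01 of 0.95. Nearly all of it is a fail under points and a pass under relative: at 6/20/70/4, SD 1.8, true values 20-60, mean r is 0.949 v 0.957.

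**The case for a change.** The strongest case for a change is prespecification. The unit is not written down, two competent programmers could build different sets from the sentence, and the set decides a pass/fail criterion. Interim counting of eligible results needs the cap as well. Printing four numbers would cost almost nothing and would match what the SAP already does for glucose and sodium.

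The imprecision stands, and so do the differing counts under skewed mixes. The rest is weaker.

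- The two readings are not equally live: the SAP's other maxima and the lack of slack at 40 per site both point to percentage points.
- The natural reading is the harder one for r, so it does not favour a pass. Moving to the relative cap after seeing results would be the visible departure, and SAP II requires revised analyses to be justified, documented and approved.
- SAP II also has sample-size counts monitored before any comparison with the criteria, so the cap has to be put into use while collection is still open.
- The skewed mixes assume that sites largely miss the chart. Protocol VI.C.1.a.i asks sites to seek all target levels and allows contrived specimens where native ones cannot be found.
- The points reading does tolerate a narrow set: as few as 40 − 14 − 24 = 2 of 40 outside 27-50, against 40 − 11 − 22 = 7 under relative. But coverage of the measuring interval is a separate requirement, and a narrow spread makes r ≥ 0.95 harder to meet.
- The chart is by site, which settles the level at which the cap applies. A filled range reads naturally as one at its maximum.

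**Conclusion.** No change follows. This is a gap in wording that an analyst fills sensibly: percentage points, by site, on the analysed set, giving caps of 25/35/60/20%. That reading is consistent with the rest of the SAP and yields an adequate set in each mix examined (150 to 300 pairs from three sites of 100). Writing down the unit would record the reading already implied; it would not correct a wrong result or bring in a better method.

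The size of the issue is conditional. Near the target mix the readings agree exactly. For the skewed mixes assumed here they differ by 45 to 72 pairs of 300 collected. The pass/fail disagreement, up to 54% in the most sensitive cell tabulated, needs an off-target mix and an error SD that places r at about 0.95. It also shrinks sharply when the outer ranges are widened, so it is not an expected consequence of the plan. The conclusion rests on the analyst reading points. A relative cap adopted without that being recorded would be a departure worth questioning when results are reported.
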